3.17 Power for analysis of secondary variable

OS will be compared between the two treatment arms, provided that the primary endpoint, PFS, is statistically significant. The power statements for overall survival below are therefore conditioned on significant primary PFS result. Estimate of first line median OS with fulvestrant alone is not published. However the median OS with fulvestrant alone in first line setting is expected to be between 34 months (letrozole alone, [Mouridsen 2003](#)) and 38 months (anastrozole alone, FACT trial, [Bergh et al 2012](#)) based on results from endocrine based monotherapy studies. For sample size calculation, we assume the median OS for fulvestrant

alone in first line to be 38 month. Median OS for fulvestrant in relapsed post-menopausal advanced breast cancer patients is estimated to be between 19 months (SoFEA trial, [Johnston et al 2013](#)) and 26 months (CONFIRM trial, [Di Leo et al 2014](#)). For sample size calculation, the median OS for fulvestrant in second line is assumed to be 26 months. Based on the expected split of first line and second line patients mentioned above, the median overall survival of control arm is estimated via simulation to be approximately 30 months. It is hypothesized that adding ribociclib to fulvestrant will result in a 29% reduction in the hazard rate for OS (corresponding to an increase in median survival to 42 months). To detect a hazard ratio of 0.71 with 85% cumulative power, a maximum of 351 deaths need to be observed, (using a log-rank test and a 3-look [superiority only] group sequential design at one-sided cumulative 2.5% level of significance). The sample size calculation was conducted with software package East 6.3.

Based on the number of patients planned to be randomized and 10% dropout rate by the time of OS final analysis, it is estimated that these 351 deaths will be observed at approximately 56 months after the randomization of the first patient. Therefore the estimated time for the final OS evaluation will be 30 months after the primary analysis of the PFS endpoint.

3.18 Sample size considerations for PK analysis

Sparse PK sampling will be performed on approximately 150 patients. Assuming a 2:1 ratio between the ribociclib and placebo arm, sparse plasma concentrations for ribociclib will be available in approximately 100 patients. Trough PK sampling will be performed in all remaining patients. PK data collected from this study may also be combined with data from other studies to support a population PK analysis of ribociclib using non-linear mixed effect modeling; details will be provided in a separate analysis plan. The choice of sampling time points was selected to ensure capture of C_{max}. The aim of this analysis is to analyze the pharmacokinetics of ribociclib in a sample size as large as possible. This sample is anticipated to represent the covariate distributions in the targeted population. No specific hypothesis will be tested and therefore no specific sample size calculation has been performed. The decisions on number of sparse PK samples and number of patients needed are driven by feasibility.

4 Details of the statistical analysis

4.1 Baseline comparability

Appropriate descriptive summary statistics of baseline variables (see [Section 3.2](#)) will be provided as in-text tables in the core CSR and also in Section 14 in the post-text tables. The summaries will be grouped by treatment arms, but no p-values will be provided.

4.2 Time-to-event analyses

The following sections present a general methodology to be used to analyze the following time-to-event variables:

- Progression-free survival
- Overall survival

- Time to definitive deterioration of the ECOG score by one category of the score from baseline
- Time to response: defined as the time between date of randomization until first documented response (CR or PR) according to RECIST
- Time to definitive deterioration of PRO scores (e.g., global health status/QoL, physical functioning, emotional functioning, social functioning scales of the EORTC QLQ-C30, and the VAS of the EQ-5D-5L)
- Time to onset of safety events
- Duration of safety events
- Time to first chemotherapy or death
- Time to first chemotherapy
- Duration of response
- [REDACTED]

4.2.1 Analysis of time-to-event data with ties

The STRATA statement in LIFETEST procedure will be used to analyze time to event data with ties. The PHREG procedure in SAS with option TIES=EXACT will be used to fit the Cox proportional hazards model.

4.2.2 Hazard ratio

The hazard ratio as a measure of treatment effect will be derived from the Cox proportional hazards model using SAS procedure PHREG with TIES=EXACT option in the MODEL statement. The stratified unadjusted Cox model will be used (where the baseline hazard function is allowed to vary across strata) for the primary analysis, i.e. the MODEL statement will include only the treatment arm variable as a covariate and the STRATA statement will include stratification variable(s).

Hazard ratio with two-sided 95% confidence interval will be based on Wald test.

4.2.3 Hypothesis and test statistic

The primary efficacy analysis will be the comparison of the distribution of PFS between the two treatment arms using a stratified log-rank test at one-sided 2.5% level of significance, i.e.,

Assuming proportional hazards model for PFS, the following statistical hypotheses will be tested to address the primary efficacy objective:

$$H_{01}: \theta_1 \geq 0 \text{ vs. } H_{a1}: \theta_1 < 0$$

where θ_1 is the log-hazard ratio (fulvestrant+ ribociclib arm vs. fulvestrant + placebo arm) of PFS.

The *stratified log-rank* test (strata based on the randomization factor from IRT) will be implemented as follows: For each of the K=4 strata, the LIFETEST procedure will be run with the STRATA statement including only the treatment variable. The TIME statement will include the survival time and a (right) censoring variable. The rank statistic S_k and the corresponding variance $var(S_k)$ (k=1, 2, 3 and 4) will be estimated from this analysis.

The final test statistics will then be reconstructed using the formula: $Z = [S1 + S2 + S3 + S4] / \sqrt{var(S1) + var(S2) + var(S3) + var(S4)}$. One-sided p-value will be computed using this Z statistic. Note: Under the null hypothesis, the asymptotic distribution of the test statistic Z is approximately normal (and correspondingly, Z^2 is approximately distributed as chi-square with one degree of freedom).

4.2.4 Kaplan-Meier estimates

An estimate of the survival function in each treatment group will be constructed using Kaplan-Meier (product-limit) method as implemented in PROC LIFETEST with METHOD=KM option. The PROC LIFETEST statement will use the option CONFTYPE=LOGLOG.

Median survival for each treatment group will be obtained along with 95% confidence intervals calculated from PROC LIFETEST output using the method of [Brookmeyer and Crowley 1982]. Kaplan-Meier estimates of the survival function with 95% confidence intervals at specific time points will be summarized. The standard error of the Kaplan-Meier estimate will be calculated using Greenwood's formula [Collett 1994].

4.2.5 Audit-based BIRC assessment of PFS

NCI method

The auxiliary variable estimator of the NCI audit-based method (Dodd et al. 2011) has the form

$$\tilde{\theta}_C = \hat{\theta}_{CA} + \hat{\lambda}(\hat{\theta}_{L\bar{A}} - \hat{\theta}_{LA})$$

where $\hat{\theta}_{CA}$, $\hat{\theta}_{L\bar{A}}$ and $\hat{\theta}_{LA}$ are estimators of the log-hazard ratio based on the central assessment in the audited subset of patients, the local assessment in the nonaudited subset of patients, and the local assessment in the audited subset, respectively. $\hat{\lambda}$ is defined as $\hat{\rho}\sqrt{\delta(1-\delta)}\sqrt{\hat{V}_{CA}/\hat{V}_L}$ and it depends on the variance estimators of $\hat{\theta}_{CA}$ (\hat{V}_{CA}) and $\hat{\theta}_L$ (\hat{V}_L) (the estimator of log-HR based on the local assessment in all patients), the proportion of patients in the audited subset (δ), and $\hat{\rho}$, an estimator of the correlation between $\hat{\theta}_{LA}$ and $\hat{\theta}_{CA}$. For the latter, a bootstrap approach will be used:

- Within the audited subset of size m , m patients will be sampled with replacement. Using this sample of m patients, the log-hazard ratio will be estimated based on the local and central assessments separately;
- This procedure will be repeated 10000 times, giving rise to 10000 pairs (local and central) of estimates of the log-HR;
- The sample correlation coefficient between these pairs of estimates will be used for $\hat{\rho}$.

The log-hazard ratio estimates contributing to the auxiliary variable estimate and corresponding variance estimates will be based on stratified Cox proportional hazards models, with stratification based on the randomization stratification factors. The upper bound of a 95% CI for θ_C will be calculated assuming asymptotic normality of $\tilde{\theta}_C$ and using the variance estimator for $\tilde{\theta}_C$ provided in Dodd et al., 2011, $\hat{V}_{CA}\{1 - \hat{\rho}^2(1 - \delta)\}$.

PhRMA method

The early discrepancy rate (EDR) and late discrepancy rate (LDR) will be calculated using the equations below together with information in [Table 4-1](#).

$$\text{EDR} = (b + a3)/(a + b);$$

$$\text{LDR} = (c + a2)/(b + c + a2 + a3).$$

Table 4-1 Local versus central disease progression assessments

Local	Central	
	PD	No PD
PD	$a = a1 + a2 + a3$	b
No PD	c	d

$a1$: number of agreements on timing and occurrence of PD

$a2$: number of times local PD declared later than central PD

$a3$: number of times local PD declared earlier than central PD

The timing of local and central response assessment will be considered to agree if they occur within ± 7 days of each other, aligned with the protocol-specified window for tumor assessments.

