2. PhRMA method: The data from the BIRC assessment generated following the sampling scheme as above will also be summarized using the method proposed by [Amit et al. 2011](#), referred to as the PhRMA (Pharmaceutical Research and Manufacturers of America) method, based on the early discrepancy rate (EDR) and late discrepancy rate (LDR). The EDR quantifies the frequency with which the investigator declares progression early relative to BIRC within each arm as a proportion of the total number of investigator assessed PDs. The LDR quantifies the frequency that the investigator declares progression later than BIRC as a proportion of the total number of discrepancies within the arm (see [Section 4.6](#) for further details). If the distribution of discrepancies is similar between the arms this suggests the absence of evaluation bias favoring a particular arm. With this approach, the differential discordance (DD) of the early discrepancy rate (EDR) and late discrepancy rate (LDR) between the two arms will be estimated as the rate on the ribociclib+fulvestrant arm minus the rate on the placebo+fulvestrant arm. The EDR and LDR results will also be summarized by treatment arm.

The following thresholds based on the NCI and PhRMA methods will be used to define the trigger for a full BIRC review:

- If the upper-bound of the one-sided 95% confidence interval for BIRC-based log-hazard ratio exceeds zero (i.e. $HR > 1$) based on the NCI method
- and/or
- If $\geq 15\%$ differential discordance is observed in EDR or LDR based on the PhRMA method.

A full BIRC review will only be considered if the primary endpoint is statistically significant. In the event of a full BIRC read of all patients' imaging data, all analyses based on BIRC assessment will be repeated including all randomized patients, with the exception of the auxiliary variable estimate (NCI method) described above.

Sensitivity analyses and further supportive analyses

As a sensitivity analysis to assess the impact of stratification, the two treatment groups will be compared using an unstratified log-rank test. The hazard ratio together with associated 95% confidence interval obtained using the unstratified Cox regression model will also be presented.

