The primary objective of the study is to compare investigator assessed PFS between arms in the overall population (both 1st line and 2nd line patients). If the primary analysis is statistically significant, treatment effect will be evaluated in 1st and 2nd line patients (i.e. previous endocrine therapy stratification factor A and B as defined in section 1.1) separately. Based on the estimated median PFS and proportion of patients in 1st line and 2nd line respectively, it is expected that the accumulation of events in 1st line will be slower than 2nd line patients. To ensure enough information coming from 1st line patients, the final analysis will be done after approximately 125 events in the first line patients or approximately 364 events in both arms whichever comes later.

Audit size for BIRC assessed PFS

The audit size of the sample-based BIRC assessment will be 40% of all randomized patients. Based on the audit size calculation approach proposed by Dodd, et. al (2011), assuming investigator and BIRC assessments are similar and the estimated log of investigator-based HR is -0.40 (i.e., HR=0.67), the audit size of 40% will ensure that the upper bound of a one-sided 95% CI for BIRC-based log-hazard ratio has 86% probability of being below 0 (i.e. HR < 1) if the correlation between investigator assessment and BIRC assessment is 0.7 (the estimated correlation based on data from the BELLE-2 [CBKM120F2302] study in metastatic breast cancer).

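### The audit weight printed in SAP 4.2.5 does not match the variance stated beside it, so the one-sided bound for the central-review PFS hazard ratio is slightly too narrow; a minor formula correction.

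*SAP*

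**What the plan says.** SAP 4.2.5 (NCI method) estimates the central-review log-hazard ratio as the central estimate in the audited patients plus lambda times a difference: the local estimate in non-audited patients minus the local estimate in audited patients. In the text as supplied, lambda "is defined as $\hat{\rho}\sqrt{\delta(1-\delta)}\sqrt{\hat{V}_{CA}/\hat{V}_L}$ and it depends on the variance estimators of" two log-hazard ratios. V_CA belongs to the central estimate in the audited subset. V_L belongs to "the estimator of log-HR based on the local assessment in all patients". Delta is the audited proportion, and rho is the bootstrap correlation of the local and central estimates within the audited subset. The upper bound assumes normality and the variance V_CA{1 - rho^2(1 - delta)}.

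The bound feeds a decision. SAP 3.8.1.4 lists two triggers for a full central read, joined by and/or. One is "If the upper-bound of the one-sided 95% confidence interval for BIRC-based log-hazard ratio exceeds zero"; the other is a differential discordance of at least 15% by the PhRMA method. A full read is considered only if primary PFS is significant.

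SAP 3.16 gives the planning case: "The audit size of the sample-based BIRC assessment will be 40% of all randomized patients". With a log-hazard ratio of -0.40 and a correlation of 0.7, the bound "has 86% probability of being below 0".

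**The concern.** The weight and the variance are printed as a pair, but the variance formula is the minimum over all weights and the printed weight is not the one that attains it. Any other weight gives a larger variance. A programmer who codes both formulas literally would therefore report a standard error that is too small and a bound that is too low for every rho above zero. The point estimate would also differ from the efficient one. What is at stake is the supportive central-review hazard ratio, its interval, and one of the two triggers for reading all patients centrally.

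**Working it through.** **Inputs.** delta = 0.40, rho = 0.7 and log-hazard ratio -0.40 (SAP 3.16, audit size); 364 events and 2:1 allocation (SAP 3.16); one-sided 95% bound, z = 1.645 (SAP 3.8.1.4).

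**Assumptions.** Information is proportional to patients, so the local variances are V_L/delta (audited) and V_L/(1 - delta) (non-audited). The two subsets are independent. For the numerical values, central and local event rates are taken as equal, so V_CA = V_L/delta.

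**Step 1: reproduce the 86%.**
- V_L = 1/(364 x 2/9) = 0.01236
- V_CA = 0.01236/0.40 = 0.03091
- Stated variance = 0.03091 x (1 - 0.49 x 0.60) = 0.03091 x 0.706, so SE = 0.1477
- P(bound below 0) = Phi(0.40/0.1477 - 1.645) = 85.6%, which rounds to the stated 86%

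**Step 2: variance for a general weight.**

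Var(lambda) = V_CA + lambda^2 V_L/[delta(1 - delta)] - 2 lambda rho sqrt(V_CA V_L/delta)

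Setting the derivative to zero gives lambda = rho*sqrt(delta)*(1 - delta)*sqrt(V_CA/V_L). Substituting it back gives exactly V_CA{1 - rho^2(1 - delta)}, the SAP's formula.

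**Step 3: put in the printed weight.** With lambda = rho*sqrt(delta(1 - delta))*sqrt(V_CA/V_L), the second term is rho^2 V_CA and the third is 2 rho^2 sqrt(1 - delta) V_CA. Hence

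Var = V_CA{1 + rho^2 - 2 rho^2 sqrt(1 - delta)}

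This exceeds the stated variance by V_CA rho^2 (1 - sqrt(1 - delta))^2, which is positive for any rho above 0.

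**Step 4: numbers at delta 0.40, rho 0.7.**
- Matching weight: 0.7 x sqrt(0.40) x 0.60 x sqrt(2.5) = 0.420
- Printed weight: 0.7 x sqrt(0.24) x sqrt(2.5) = 0.542, which is 29% larger
- True variance with the printed weight: 1 + 0.49 - 0.98 x 0.7746 = 0.731 V_CA, SE 0.1503
- SE ratio: 0.1503/0.1477 = 1.017
- One-sided coverage: Phi(1.645/1.0175) = 94.7%
- Upper bound at log-hazard ratio -0.40: HR 0.855 with the stated SE, 0.858 with the true SE

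A simulation of 2 million draws agreed: variance 0.732 V_CA and coverage 94.7% with the printed weight, 0.707 V_CA and 95.0% with the matching weight.

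**Step 5: sensitivity to rho (delta 0.40).**

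| rho | stated variance / V_CA | true variance, printed weight / V_CA | SE ratio | coverage |
|---|---|---|---|---|
| 0.5 | 0.850 | 0.863 | 1.007 | 94.9% |
| 0.7 | 0.706 | 0.731 | 1.017 | 94.7% |
| 0.9 | 0.514 | 0.555 | 1.039 | 94.3% |

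**Step 6: how near zero the bound must be.** For a given point estimate, the SE error moves the bound by 1.645 x (0.1503 - 0.1477) = 0.004 on the log scale. The weight also moves the point estimate, by (0.542 - 0.420) times the local difference between subsets. That difference has mean zero under random sampling and SD sqrt(0.01236/0.24) = 0.227, so the typical shift is 0.122 x 0.227 = 0.028. At planning values the trigger could therefore differ only when the bound lies within a few hundredths of zero.

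**The case against.** The strongest objection is provenance. The printed and matching weights contain the same symbols in the same order and differ only in whether the first square root covers delta alone or delta(1 - delta). The text was read from a PDF by a program, and the length of a radical bar is easily misread. The variance formula and the 86% both fit the matching weight, which suggests a typesetting or reading slip. This stands as a caution: it is unproven, but if the source shows the root over delta alone, the point falls away. The cited method paper was not available, so the check rests on the SAP's own definitions.

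The second objection is size, and it also stands. Central-review PFS is supportive only, the trigger is one of two, and it applies only after a significant primary result. Protocol 7.2.1.3 records the central review as completed, and Protocol 10.4.4 plans no further formal PFS analyses.

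A reader might infer more than the documents support:
- **That the 86% is wrong.** It follows from the stated variance (85.6%). The printed weight gives 85.2% with the stated variance and 84.5% with its own, but neither figure shows an error in the planning statement.
- **That the decision on a full read was wrong, or that the central estimate is biased.** Nothing shows which weight was coded, and the estimator stays centred for any fixed weight because the local difference has mean zero under random sampling.
- **That the bound might be two-sided,** since 4.2.5 omits the word one-sided. SAP 3.8.1.4 and 3.16 both specify a one-sided 95% interval.

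**Conclusion.** As printed, the weight and the variance in SAP 4.2.5 are inconsistent, and the direction is certain under the stated assumptions: the bound is too narrow for any positive rho. The size is small. At the planning values the SE is understated by 1.7% and one-sided coverage falls by 0.3 percentage points. The primary PFS test is not affected. The conclusion rests on information proportional to patients, independent subsets, and the radical extending as it appears in the supplied text. This is a minor formula correction, not a threat to the central-review conclusion.

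**What to change.** First confirm in the source PDF and in the executed program how far the radical extends. If the root covers delta only, no change is needed.

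If the printed form was used, write the weight as rho*sqrt(delta)*(1 - delta)*sqrt(V_CA/V_L) and keep the stated variance. Equivalently, keep sqrt(delta(1 - delta)) and replace V_L with the variance of the local estimate in non-audited patients: since that variance is V_L/(1 - delta), the two weights are the same. Keeping the printed weight with its own variance from Step 3 would also be consistent, though less efficient. Then rerun the audit estimate and its bound, and record the correction.

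The cost is one formula, one line of code and one rerun.

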4.3 Group sequential design used in Phase III studies

The statistical methodology for the interim analyses of OS will be based on group sequential methodology with efficacy stopping boundaries defined by type I error spending functions.

This approach is flexible in dealing with any deviations from the targeted event totals, or unexpected changes to the plan.

If the exact number of events observed at the interim and final analyses deviates from the target numbers described in the protocol, the actual critical boundaries will be derived using the pre-specified error spending functions and the actual numbers of events observed.

- At interim analyses, information fractions will be computed as the ratio of the number of events observed at the considered interim analysis relative to the number targeted for the final analysis, as described in the sample size section of the protocol.
- At the final analysis, the critical value will be calculated using the exact number of observed events at the final cut-off date, considering the α -levels spent at interim analyses and considering the actual correlation among the test statistics, in order to achieve a cumulative type I error smaller than the desired significance level (i.e. smaller than 2.5% for a one-sided test and smaller than 5% for a two-sided test).

4.3.1 Alpha-spending function

The stopping boundaries to be used for OS test will be calculated using the α -spending function approach described in Lan and DeMets ([Lan and DeMets, 1983](#)). The spending function for one-sided test has the following functional form:

$$\alpha(t) = 2 - 2\Phi(Z_{\alpha/2} / \sqrt{t})$$

This function generates stopping boundaries that closely resemble the O'Brien-Fleming boundaries (O'Brien and Fleming, 1979).

4.4 Duration of follow-up

Study follow-up will be summarized using the following methods:

- Summary of duration between randomization and cut-off date, and follow-up times for primary PFS/OS, which are defined as follows:
 - Randomization (recruitment) period = (Date of last patient randomized - Date of first patient randomized + 1) / 30.4375 (months)
 - Duration between randomization and data cut-off date = (Cut-off date - Date of randomization + 1) / 30.4375 (months). This item will be summarized overall.
 - Follow-up time = (Date of event or censoring - Date of randomization + 1) / 30.4375 (months) regardless of censoring. Date of censoring is defined as the last adequate tumor assessment date for PFS or last contact date for OS. This item will be summarized by treatment arm.

All summaries will be reported in months. Date of censoring is the same as defined for the PFS and OS analysis.

In addition, the time from PFS/OS censoring date to data cut-off date will be summarized by time intervals in months: <3, 3 - < 6, 6 - < 12, 12 - < 18, 18 - <24 and by 12 month intervals thereafter if necessary. The gap time is calculated as (([analysis cut-off date] - [censoring date] + 1)/30.4375

